9.5.3 Analyses of Exploratory Efficacy Endpoint(s)

Not applicable.

9.6 Safety Analyses

9.6.1 Analyses of Primary Safety Endpoint(s)

Not applicable.

9.6.2 Adverse Events

The Medical Dictionary for Regulatory Activities (MedDRA) version 27.0 or later is used to code all events categorized as adverse events to a system organ class and a preferred term.

The subject incidence of adverse events will be summarized for all TEAEs, TRAEs, serious TEAEs, grade 3 or higher TEAEs, fatal TEAEs, TEAEs leading to withdrawal of tarlatamab, TEAEs leading to interruption and/or reduction of tarlatamab. Subject incidence summary by system organ class and preferred term in descending order of frequency will be provided for all TEAEs, TRAEs, serious TEAEs, grade 3 or higher TEAEs, fatal TEAEs, TEAEs leading to withdrawal of tarlatamab, TEAEs leading to interruption and/or reduction of tarlatamab. Where appropriate the summary will also be provided by worst grade. Above summaries will not be created if two or fewer subjects experience the AE, subject-level data may be provided instead.

Severity of CRS and ICANS events will be graded using American Society for Transplantation and Cellular Therapy (ASTCT) (Lee et al, 2019) criteria. Severity of tumor lysis syndrome (TLS) will be graded using CTCAE version 5.0 but will be managed based on Cairo Bishop criteria ([Coiffier et al, 2008](#)). Severity of all other adverse events will be graded using CTCAE version 5.0.

Subject incidence of events of interest (standardized MedDRA queries and/or Amgen Medical Queries) will also be summarized according to their categories and preferred term if appropriate.

Adverse Events of Interest (EOI):

The summary of subject incidence of treatment-emergent adverse events of interest standardized MedDRA queries and/or Amgen Medical Queries such as cytokine release syndrome, hypersensitivity, immune effector cell associated neurotoxicity syndrome (ICANS) and associated neurological events, neutropenia, and neurological events will be summarized. The summary will include grade \geq 2, grade \geq 3, grade \geq 4, serious, fatal, and events leading to interruption and/or reduction and discontinuation of IP.

The subject incidence of above treatment-emergent EOIs, serious treatment-emergent EOI, grade 3 or higher treatment-emergent EOI, fatal treatment-emergent EOI, treatment-emergent EOI leading to discontinuation of investigational product and treatment-emergent EOI leading to interruption and/or reduction of

investigational product will be tabulated by preferred term. CRS and immune-effector cell-associated neurotoxicity syndrome (ICANS) will be graded according to American Society for Transplantation and Cellular Therapy (ASTCT) ([Lee et al. 2019](#)).

The summaries of time to onset of EOI from first dose, time to onset of EOI after each dose from last prior dose, and duration of treatment-emergent EOI will be provided. Additionally, summaries of time to onset and duration of EOI will be provided for grade 2 or higher and grade 3 or higher EOIs respectively.

9.6.3 Exposure to Investigational Product

Subject exposure to tarlatamab will be summarized using descriptive statistics for the following: number of doses, cumulative dose (mg), relative dose intensity (%), treatment duration (weeks) and number and percent of subjects with dose modifications (e.g dose reductions, dose interruptions) and reason for modification. Subject-level data may be provided instead of the summary if the subject incidence is low, or a single dose is given. Listing of the unique manufacturing lot numbers, and a listing of the subjects administered each manufacturing lot number will be provided.

9.6.4 Laboratory Test Results

Laboratory data will be summarized using standard descriptive statistics at each scheduled time point in the study. Summaries of the absolute value and/or changes from baseline at each scheduled assessment will be provided for selected laboratory parameters of interest.

Shift tables indicating the change between the baseline and the worst on-study increased and/or decreased grade will be provided for selected laboratory parameters of interest. Unscheduled assessments will be included in the shift tables.

The subject incidence of potential cases of Hy's Law will be summarized. Hy's law cases have the following three components: **A potential Hy's Law case is defined as any postbaseline total bilirubin elevation to $\geq 2 \times$ ULN occurring on or within 30 days after a postbaseline ALT or AST elevation to $\geq 3 \times$ ULN and concurrent ALP $< 2 \times$ ULN.** A listing of AST, ALT, and Total Bilirubin values at each time point may be produced for the subjects suspected of fulfilling the criteria for Hy's law.

9.6.5 Vital Signs

Vital signs including systolic/diastolic blood pressure, heart rate, respiratory rate, pulse oximetry and temperature will be summarized by summary statistics over time and

changes from baseline over time using descriptive statistics. The incidence and percentage of abnormal changes in vital signs will be tabulated.

9.6.6 Physical Measurements

The analysis will include descriptive summary at baseline.

9.6.7 Electrocardiogram

The ECG measurements are performed as per SOC for routine safety monitoring, rather than for assessment of potential QTc effect. No statistical analyses of ECG measurements are planned.

9.6.8 Antibody Formation

The incidence and percentage of subjects who develop anti-tarlatamab antibodies at any time will be tabulated.

9.6.9 Exposure to Non-investigational Product(s)/Auxiliary Medicinal Product(s)

Not applicable.

9.6.10 Exposure to Concomitant Medication

The number and proportion of subjects receiving therapies of interest will be summarized by preferred term or category as coded by the World Health Organization Drug (WHO DRUG) dictionary.

9.7 Other Analyses

The following additional analysis will be provided by the Department of Clinical Pharmacology, Modeling and Simulation (CPMS). This data may be analyzed at a later date.

9.7.1 Analyses of Pharmacokinetic or Pharmacokinetic/Pharmacodynamic Endpoints

For tarlatamab, PK parameters will be determined from the time concentration profile using standard non-compartmental approaches and considering the profile over the complete sampling interval. Based on the review of the data, exploratory analyses to describe the relationship between tarlatamab exposure and either PD effect and/or clinical outcome may also be performed. These exploratory analyses may not be part of the clinical study report.

9.7.2 Analyses of Clinical Outcome Assessments

Not applicable.

9.7.3 Analyses of Health Economic Endpoints

Medical resource utilization data collected may be used to conduct following analyses:

- Number and duration of hospitalization (total days or length of stay, including duration by wards, e.g., intensive care unit)
- Number and type of diagnostic and therapeutic tests and surgical and nonsurgical procedures.
- Reason for hospitalization (e.g., adverse event such as CRS/ICANS or other).

9.7.4 Analyses of Biomarker Endpoints

Not applicable.

10. Changes From Protocol-specified Analyses

Protocol section 9.4.2.3.7 mentions of summarizing the following for analysis of exposure to investigational product: average dose per administration. But it will not be summarized. SAP section 9.6.3 outlines the analysis. **Protocol sections 1.1 and 3.0 defined the PFS, OS and DoDC defined as time from enrollment date. But it will be considered from the date of first dose of tarlatamab. SAP section 5 outlined the analysis.**

11. Literature Citations / References

Coutinho AD, Shah M, Lunacsek OE, Eaddy M, Willey JP. Real-world treatment

patterns and outcomes of patients with small cell lung cancer progressing after 2 lines of therapy. *Lung Cancer*. 2019;127:53-58.

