
 Evaluate efficacy of tarlatamab as assessed by objective response rate (ORR) based on blinded independent central review (BICR) per Response Evaluation Criteria in Solid Tumors version 1.1 (RECIST 1.1) 	
 ORR BICR, defined as proportion with best overall response (BOR) of complete response (CR) plus partial response (PR)
Secondary	

 Evaluate efficacy of Tarlatamab as assessed by duration of response (DOR), disease control (DC), and progression-free survival (PFS) based on BICR per RECIST 1.1 	
 DOR, defined as time from the first documentation of objective response (OR) until the first documentation of disease progression or death due to any cause, whichever occurs first. Only subjects who have achieved OR will be evaluated for DOR DC, defined as CR + PR + stable disease (SD) Duration of DC, defined as time from the first documentation of CR, PR, or SD until the first documentation of disease progression or death due to any cause, whichever occurs first. Only subjects who have achieved CR, PR, or SD will be evaluated for Duration of DC PFS, defined as time from enrollment until disease progression or death from any cause, whichever occurs first. Progression will be based on RECIST 1.1.

 Evaluate efficacy of Tarlatamab as assessed by ORR, DOR, DC, and PFS based on investigator assessment per RECIST 1.1 	
 ORR (Investigator) DOR DC Duration of DC PFS

 Evaluate efficacy of Tarlatamab as assessed by overall survival (OS) 	
 OS, defined as time from enrollment until death from any cause

• Evaluate safety and tolerability	
• Incidence of treatment-emergent adverse events

• Characterize the pharmacokinetics of tarlatamab	
• Serum concentration of tarlatamab

• Evaluate the immunogenicity of tarlatamab	
• Incidence of anti-tarlatamab antibody formation

Estimand(s) for Primary Objective(s)

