
 Evaluate efficacy of tarlatamab as assessed by objective response rate (ORR) based on blinded independent central review (BICR) per Response Evaluation Criteria in Solid Tumors version 1.1 (RECIST 1.1) 	
 ORR BICR, defined as proportion with best overall response (BOR) of complete response (CR) plus partial response (PR)
Secondary	

 Evaluate efficacy of Tarlatamab as assessed by duration of response (DOR), disease control (DC), and progression-free survival (PFS) based on BICR per RECIST 1.1 	
 DOR, defined as time from the first documentation of objective response (OR) until the first documentation of disease progression or death due to any cause, whichever occurs first. Only subjects who have achieved OR will be evaluated for DOR DC, defined as CR + PR + stable disease (SD) Duration of DC, defined as time from the first documentation of CR, PR, or SD until the first documentation of disease progression or death due to any cause, whichever occurs first. Only subjects who have achieved CR, PR, or SD will be evaluated for Duration of DC PFS, defined as time from enrollment until disease progression or death from any cause, whichever occurs first. Progression will be based on RECIST 1.1.

 Evaluate efficacy of Tarlatamab as assessed by ORR, DOR, DC, and PFS based on investigator assessment per RECIST 1.1 	
 ORR (Investigator) DOR DC Duration of DC PFS

 Evaluate efficacy of Tarlatamab as assessed by overall survival (OS) 	
 OS, defined as time from enrollment until death from any cause

 Evaluate safety and tolerability 	
 Incidence of treatment-emergent adverse events

 Characterize the pharmacokinetics of tarlatamab 	
 Serum concentration of tarlatamab

Evaluate the immunogenicity of tarlatamab	
Incidence of anti-tarlatamab antibody formation
---	---

Estimand(s) for Primary Objective(s)

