5.4 Subject Enrollment

Before subjects begin participation in any study-specific activities/procedures, Amgen requires a copy of the site's written external review bodies (eg, the institutional review board [IRB]/independent ethics committee[IEC]/regulatory authorities) approval of the protocol, informed consent form (ICF), and all other subject information and/or recruitment material, if applicable (see [Section 11.3](#)).

The subject or the subject's legally authorized representative and the investigator or authorized delegate must personally sign and date the external review body informed consent before commencement of study-specific procedures.

Each subject who enters the screening period for the study (defined as the point at which the subject signs the informed consent) receives a unique subject identification number before any study-related activities/procedures are performed. The subject identification number will be assigned using IRT. This number will be used to identify the

subject throughout the clinical study and must be used on all study documentation related to that subject.

The subject identification number must remain constant throughout the entire clinical study; it must not be changed after initial assignment, including if a subject is rescreened.

Subjects are eligible to be enrolled in the study when the investigator confirms that the subject has met all eligibility criteria. Subjects are considered enrolled at the time of first dose of investigational product administration. The investigator is to document enrollment decision and date, in the subject's medical record and in/on the Subject Enrollment Case Report Form (CRF) via IRT.

Sites that do not enroll subjects within 6 months of site activation may be closed.

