2.1 Objectives and Endpoints/Estimands

Objectives	Endpoints
Primary	

Evaluate efficacy of tarlatamab as assessed by objective response rate (ORR) based on blinded independent central review (BICR) per Response Evaluation Criteria in Solid Tumors version 1.1 (RECIST 1.1)	
ORR BICR, defined as proportion of subjects with best overall response (BOR) of complete response (CR) or partial response (PR)
Secondary	

Evaluate efficacy of Tarlatamab as assessed by duration of response (DOR), disease control (DC) and progression-free survival (PFS) based on BICR per RECIST 1.1	
DOR, defined as time from the first documentation of objective response (OR) until the first documentation of disease progression or death due to any cause, whichever occurs first. Only subjects who have achieved OR will be evaluated for DORDC, defined as a BOR of CR or PR or stable disease (SD)Duration of DC, defined as time from the first documentation of CR or PR or SD until the first documentation of disease progression or death due to any cause, whichever occurs first. Only subjects who have achieved CR or PR or SD will be evaluated for duration of DCPFS, defined as time from enrolment until disease progression or death from any cause, whichever occurs first. Progression will be based on RECIST 1.1.

Evaluate efficacy of Tarlatamab as assessed by ORR, DOR, DC and PFS based on investigator assessment per RECIST 1.1	
ORR (Investigator)DOR (Investigator)DC (Investigator)Duration of DC (Investigator)PFS (Investigator)

Evaluate efficacy of Tarlatamab as assessed by overall survival (OS)	
OS, defined as time from enrolment until death from any cause

Evaluate safety and tolerability	
Incidence of treatment-emergent adverse events

Characterize the pharmacokinetics of tarlatamab	
Serum concentration of tarlatamab

Evaluate the immunogenicity of tarlatamab	
Incidence of anti-tarlatamab antibody formation

Estimand(s) for Primary Objective(s)

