5.2 Efficacy Endpoint-related Definitions

Best Overall Response (BOR)

The subject's best response assignment depends on the findings of both target and non-target disease and also takes into consideration the appearance of new lesions and confirmation of response based on the findings from MRI/CT scans. Confirmation of progressive disease is not required. BOR is based on all post-baseline disease assessments that occur prior to the initiation of subsequent anticancer treatment. At least 5 weeks from the first dose of IP must elapse without radiological disease progression to meet the minimum criteria for SD duration in order to assign a BOR of SD. In general, subjects not classifiable under the RECIST 1.1 response categories due to inadequate data or early death are classified as not evaluable (NE) for BOR but will be counted in the denominator of all response rate calculations. BOR per RECIST 1.1 has the following possible categories: complete response (CR), partial response (PR), stable disease (SD), progressive disease (PD), not evaluable (NE). The rules for deriving the BOR are detailed in Appendix B.

Objective Response (OR)

OR is defined as a BOR of CR or PR per RECIST 1.1. Subject without a post-baseline tumor assessment is considered non-responder.

Objective Response Rate (ORR)

ORR is defined as proportion of subjects with BOR of CR or PR per RECIST 1.1.

Disease Control (DC)

DC is defined as a BOR of CR or PR or SD per RECIST 1.1.

Disease Control Rate (DCR)

DCR is defined as proportion of subjects with a BOR of CR or PR or SD per RECIST 1.1.

Duration of Disease Control (DoDC)

DoDC is defined as time from **the date of first dose of tarlatamab** until the first documentation of disease progression or death due to any cause, whichever occurs first. Only subjects with a BOR of confirmed response (CR/PR) or SD are evaluated for DoDC.

DoDC (Months) = (earlier of progressive disease date or death date – **date of first dose of tarlatamab** + 1) × 12 / 365.25

DoDC is censored following the same censoring rules as PFS ([Appendix C](#)).

Duration of Response (DOR)

DOR is defined as time from first documentation of CR or PR per RECIST 1.1 until the first documentation of progressive disease or death due to any cause, whichever occurs first. Only subjects who with a BOR of confirmed response (CR/PR) are evaluated for DOR.

DOR (Months) = (earlier of progressive disease date or death date – response start date + 1) × 12 / 365.25

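### SAP section 10 misstates the protocol's starting point for duration of disease control, so a shift of about six weeks that moves subjects across the 4-month benefit threshold reads as no change at all

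*SAP*

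**What the plan says.** Protocol section 1.1 gives the secondary endpoint as "Duration of DC, defined as time from the first documentation of CR, PR, or SD until the first documentation of disease progression" or death, and Protocol section 3 repeats it. SAP 2.1 carries the same origin forward: "Duration of DC, defined as time from the first documentation of CR or PR or SD".

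SAP 5.2 then starts DoDC at the first dose of tarlatamab. Its formula opens "DoDC (Months) = (earlier of progressive disease date or death date"; it goes on to subtract the first-dose date, add one day and convert to months by 12/365.25. SAP 5.2 limits DoDC to subjects whose best overall response is confirmed CR or PR, or SD, and applies the PFS censoring rules of Appendix C.

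SAP section 10 explains the difference with the statement "Protocol sections 1.1 and 3.0 defined the PFS, OS and DoDC defined as time from enrollment date". It says first dose will be used instead and points to SAP section 5. Protocol 5.4, however, fixes enrollment as follows: "Subjects are considered enrolled at the time of first dose of investigational product administration".

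Both documents report the percentage of subjects with DoDC of at least 4 months (Protocol 9.4.2.2, SAP 9.5.2). The protocol presents it as the summary of clinical benefit.

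**The concern.** The section meant to record departures from the protocol describes one that did not happen and misses the one that did. Read with Protocol 5.4, a move from enrollment to first dose has no effect on any endpoint, so a reader would pass over it. For PFS and OS that is right. For DoDC the origin has moved back from the first scan showing control to the first dose.

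The added weeks are event-free by construction: a subject enters the DoDC analysis only by reaching a scan without progression. The change therefore lengthens every DoDC value and can only raise the 4-month percentage. It also leaves DoDC with the same origin, formula and censoring as PFS, so it becomes PFS restricted to subjects with disease control. In a single-arm trial of about 30 subjects, a benefit rate of this kind is likely to be set beside figures from elsewhere, and its origin has to be clear.

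**Working it through.** The plan states no expected DoDC and no expected 4-month rate, so it has no figure of its own to reproduce on this point. The sample-size table concerns ORR only.

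**Inputs**
- Scans every 6 weeks ± 1 week to week 48, timed from the first dose (Protocol 1.3). With first dose as study day 1, nominal scans fall on days 43, 85, 127 and 169; an in-window first scan falls on days 36 to 50.
- Month formula (SAP 5.2): (end − start + 1) × 12/365.25.
- Threshold: 4 months (Protocol 9.4.2.2, SAP 9.5.2).
- For illustration only: median PFS 4.9 months, 95% CI 2.9 to 6.7, in the 10 mg group of the earlier phase 2 study (Protocol 2.3).

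**Step 1: the origins side by side**

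| Place | Start of DoDC |
|---|---|
| Protocol 1.1 and 3 | First documentation of CR, PR or SD |
| SAP 2.1 | First documentation of CR, PR or SD |
| SAP 5.2 | First dose |
| SAP 10, describing the protocol | Enrollment, which is first dose under Protocol 5.4 |

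**Step 2: size of the shift.** First documentation at the nominal first scan: 43 − 1 = 42 days, and 42 × 12/365.25 = 1.38 months. Across the scan window it is 35 to 49 days (1.15 to 1.61 months). It is longer if the first scan is missed or not evaluable.

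**Step 3: the threshold in days.** 4 × 365.25/12 = 121.75, so 122 days counted inclusively.
- From first dose: the event must fall on study day 122 or later.
- From first documentation on day 43: on day 43 + 122 − 1 = 164 or later (157 to 171 across the window).

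Subjects with an event on about days 122 to 163 meet the threshold only under SAP 5.2.

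**Step 4: progression at scheduled scans, first documentation on day 43**

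| PD at | Study day | From first dose | From first documentation |
|---|---|---|---|
| Week 12 | 85 | 85 × 12/365.25 = 2.79, fails | 43 × 12/365.25 = 1.41, fails |
| Week 18 | 127 | 127 × 12/365.25 = 4.17, meets | 85 × 12/365.25 = 2.79, fails |
| Week 24 | 169 | 169 × 12/365.25 = 5.55, meets | 127 × 12/365.25 = 4.17, meets |

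The window matters at the edges. A week-18 scan on day 120 gives 3.94 months from first dose and fails under both origins. A week-24 scan on day 162 gives 5.32 versus 3.94 months and changes status.

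**Step 5: illustration of the 4-month rate.** Assume exponential event times, no censoring, and condition on being event-free at week 6 (42 days after first dose). With median 4.9 months, λ = ln 2/(4.9 × 30.4375) = 0.00465 per day.
- From first dose: S(121)/S(42) = exp(−79λ) = 0.693.
- From first documentation: S(163)/S(42) = exp(−121λ) = 0.570.

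If progression is dated only at nominal scans, progression after week 12 is dated at week 18 or later, and progression after week 18 at week 24 or later:
- From first dose: S(84)/S(42) = exp(−42λ) = 0.823.
- From first documentation: S(126)/S(42) = exp(−84λ) = 0.677.

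| Median PFS (months) | Continuous dating | Gap (points) | Scan dating | Gap (points) |
|---|---|---|---|---|
| 2.9 | 53.8% vs 38.7% | 15.1 | 71.9% vs 51.7% | 20.2 |
| 4.9 | 69.3% vs 57.0% | 12.3 | 82.3% vs 67.7% | 14.6 |
| 6.7 | 76.5% vs 66.3% | 10.2 | 86.7% vs 75.2% | 11.5 |

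If 15 to 24 of the 30 subjects have disease control (an assumption), the number changing status runs from 15 × 0.102 = 1.5 to 24 × 0.202 = 4.8, or about 2 to 5.

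**The case against.** The best defence is that the change is on the record. SAP 10 names DoDC, gives first dose as the new origin and points to section 5, where the only DoDC formula stands. A reader might infer that the sponsor concealed a favourable change; the documents do not support that. What is wrong is the account of the former origin, and with it the apparent size of the change. Nor is it likely that two programmers would part ways: one who reads section 10 will follow 5.2. The wording left in 2.1 is an alignment error, though a real one.

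First dose is also a coherent origin. Both documents already measure the minimum duration of SD from first dose, so one may time disease control the same way. This stands, and it means the documents do not show that the protocol origin must be the leading result.

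The effect is bounded. Six weeks is the nominal figure, only subjects with disease control are affected, and only events between the two cut-offs change status. ORR, DCR, DOR, PFS and OS are untouched, and no hypothesis is tested. The rates in the illustration depend on the model. The scan-dated version may count detection delay twice, because a reported median PFS will usually reflect scan dates already. It would also be wrong to quote these rates over all treated subjects, since SAP 5.2 evaluates DoDC only in those with CR, PR or SD.

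None of this repairs the false statement in section 10 or the conflict between 2.1 and 5.2.

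**Conclusion.** The point holds as an error of description and an internal conflict, not as a concealed change or a wrong choice of origin. SAP 10 attributes to the protocol a DoDC origin that it does not have, and the SAP defines the endpoint in two ways.

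The text alone settles the shift of about 42 days (35 to 49 with an in-window first scan), the change of status for events on about days 122 to 163, and the nominal week-18 example. The difference in rates is an illustration: a gap of about 12 points at median 4.9 months and 10 to 15 over the quoted interval for the median, or about 15 (11 to 20) if progression is dated only at scans. It rests on exponential event times, no censoring, a nominal first scan and conditioning on being event-free at week 6. The direction does not depend on the model: the first-dose origin never gives the lower rate.

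**What to change.** - Correct SAP section 10 so that it treats DoDC apart from PFS and OS, and says that its origin moves from first documentation of CR, PR or SD (Protocol 1.1 and 3) to first dose. Note that for PFS and OS the change has no effect, because enrollment is the first dose.
- Make SAP 2.1 and 5.2 give the same DoDC origin.
- In SAP 9.5.2, report the percentage with DoDC of at least 4 months from both origins, each labelled, for the central and the investigator assessments. Which one leads is the sponsor's choice, to be stated before database lock.

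The cost is a few sentences in the SAP and one extra table row for each assessment. No new data are needed. The figure from first documentation will be equal or less favourable, and showing both lets a reader see by how much.
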